#### Study Design

Patients will enroll in the study online. The on-line experience has been carefully designed to mimic the experience of buying the device in a retail store or on a website without consulting a sleep professional or dentist. After filling out a short online questionnaire to determine their initial symptoms and signing the informed consent, the product and instructions will be shipped to them. The device is used for a period of 10 days in the clinical trial. An email prompting them to complete a follow-up questionnaire will be sent ten days after the device has been received. Upon completion of the follow-up survey, the cost of the device will be refunded to the patient, incentivizing completion of the study.

The surveys will ask the patients to qualitatively and quantitatively compare their snoring before use of the device and after 10 days of using the device.

As part of the follow-up survey, users will be asked if they self-identified (on the basis of the product instructions) as being at risk for OSA. If they answer positively, they will be asked about their response, including whether they sought medical care, enrolled in a sleep study, or discontinued use of the device.

A two-sample t-test will be used to analyze the change from the initial survey to the follow-up survey, with patients serving as their own controls.

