## II. Purpose and Background

The purpose of this study is to evaluate the safety and efficacy of an over-the-counter (OTC) intraoral mouthpiece to reduce snoring. A secondary objective is to evaluate the behavior of patients at high risk for sleep apnea to determine whether they will seek a conclusive diagnosis with a sleep study.

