## Obstructive Sleep Apnea (OSA)

Obstructive Sleep Apnea (OSA) is a sleep disorder where breathing stops and restarts multiple times during the night, interrupting sleep and often abruptly awakening the patient with a feeling of suffocation. There is significant overlap between snoring and patients with obstructive sleep apnea, which is estimated to affect 3-7% of men and 2-5% of women (Punjabi NM, *The Epidemiology of Adult Obstructive Sleep Apnea*, Proceedings of American Thoracic Society, 5:2, 2008).

The vast majority of those with sleep apnea also habitually snore, though the majority of habitual snorers *do not* have sleep apnea. From prevalence estimates, approximately 10% of male and 22% of female snorers may also have OSA. Women are eight times more likely to have their OSA undiagnosed than men.

The instructions for use of the mouthpiece helps the patient assess their risk of mild, moderate or severe OSA and may encourage them to register for an inexpensive home sleep study. It is hoped that this device may help some habitual snorers identify their risk of OSA and seek treatment. This clinical trial will also monitor the behavior of these users, looking to see whether they i) seek a sleep study, ii) return the device for a refund or iii) decide to use the snoring device. In the first two cases, they will be dropped from the clinical trial.

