## Methods and Procedures

## Methods and Procedures

Subjects who are interested in reducing their snoring will be recruited online. In order to participate in the trial, they will complete a pre-trial questionnaire, as well as review and sign the Informed Consent.

Assuming they satisfy the Inclusion and Exclusion criteria and sign the Informed Consent (includes the inclusion/exclusion criteria), they will purchase the device for \$90. The intraoral device and patient instructions will be mailed to them (Attachment E).

Once the subject is able to participate in the study, the device is placed in boiling water to soften it. While still warm, the device is placed in the mouth and molded to the individual patient. This is the same procedure used with many intraoral mouthpieces and devices including the Zyppah Boil and Bite.

The subject will be asked to use the intraoral device each night for ten consecutive nights. After they have used the device for ten days, a follow-up survey will be emailed to the subject. The patient will respond to the questions in the survey. After they have completed the follow-up survey and returned it, the subject will receive a full refund for the cost of the device (\$90). This is intended to increase compliance with the protocol.

This study will also evaluate the response of subjects who are at high risk of obstructive sleep apnea. The product instructions will contain a brief questionnaire (Attachment D, STOP-BANG Survey) assessing the subject's risk for OSA. If they are determined to be high-risk by the self-administered questionnaire, they will be given the following options: 1) complete a full, overnight in-office sleep study, 2) complete a discounted in-home sleep study, or 3) discontinue use of the device and return it for a full refund. The response of these subjects will be monitored to see how they respond and whether they continue to use the device or seek medical attention to evaluate their risk of sleep apnea.

This is a non-significant risk study, and the only 'extra' requirements for this study are the completion of the pre-study and post-study questionnaires by the patient.

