# Data Collection

- Attachment A is the list of questions to gather personal information about the subject, including age, gender, weight, height and contact information. This will allow for the calculation of Body Mass Index (BMI), a well-known risk factor in both snoring and obstructive sleep apnea. This attachment also contains the Inclusion/Exclusion criteria, where potential subjects will be asked to review and certify that they meet the requirements of the trial (they will also see this information later in the process at the Informed Consent).
- Attachment B is the Visual-Analog Scale (VAS) asking potential subjects how much their snoring is bothering them and their partner (if applicable). The VAS method is commonly used and has been validated for patient satisfaction (Brokelman et al, 2012).
- Attachment C is the Snoring Severity Scale (SSS). This validated, three-question survey has been shown to accurately assess the severity of snoring and the risk for obstructive sleep apnea (Morris L et al, 2008)
- Attachment D is the Stop-Bang Assessment, which is the most frequent assessment used to determine the risk of sleep apnea. This 8-question survey has been validated as a risk assessment for moderate to severe sleep apnea (Nagappa et al, 2015).

The pre-questionnaire will consist of Attachments A, B, and C to establish a baseline. The postquestionnaire will consist of Attachments B, C, and D, also allowing the study to evaluate the response of subjects at high risk of OSA.

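### Sleep-study seeking is asked only of respondents who say they recognised their own OSA risk, so the seeking rate among all high-risk subjects cannot be estimated

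*Combined protocol and SAP*

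**What the plan says.** Section II (Purpose and Background) gives the secondary objective as to "evaluate the behavior of patients at high risk for sleep apnea to determine whether they will seek a conclusive diagnosis with a sleep study". It does not restrict this to patients who have recognised their risk.

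Under Study Design, the follow-up survey starts with a filter: "users will be asked if they self-identified (on the basis of the product instructions) as being at risk for OSA". The questions on behaviour come only after a yes: "If they answer positively, they will be asked about their response, including whether they sought medical care, enrolled in a sleep study", or stopped using the device.

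Data Collection places the STOP-BANG form (Attachment D) in the follow-up questionnaire with no such filter: "The postquestionnaire will consist of Attachments B, C, and D, also allowing the study to evaluate the response of subjects at high risk of OSA".

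Methods and Procedures also puts STOP-BANG in the product instructions, for self-scoring: "If they are determined to be high-risk by the self-administered questionnaire, they will be given the following options". It adds: "The response of these subjects will be monitored to see how they respond and whether they continue to use the device". It describes no means of monitoring other than the survey.

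The Obstructive Sleep Apnea (OSA) section lists three outcomes for at-risk users: seeking a sleep study, returning the device, or using it. Of these it says: "In the first two cases, they will be dropped from the clinical trial". Data Analysis and Monitoring counts discovery of moderate to severe apnea within the 30% dropout.

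No section defines a numerator, denominator or analysis for the seeking rate.

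**The concern.** The trial imitates an over-the-counter purchase with no professional involved. The Background section raises the worry that such a device may keep people with OSA from being tested. Whether unsupervised users notice their own risk is therefore part of what the secondary objective should show.

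A subject who skipped, mis-scored or ignored the questionnaire in the instructions will answer no to the filter question. If that subject scores high on STOP-BANG minutes later, the study will know that a high-risk person did not recognise the risk. It will not know whether that person saw a doctor, had a sleep study or stopped using the device. This is the user the over-the-counter worry is about, and the survey as described collects no outcome from them. Unless the items are asked at follow-up, the survey data cannot supply the answer later.

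**Working it through.** The plan states no seeking rate, precision or sample size for the secondary objective, so there is no figure to reproduce. The check is of what the survey can estimate, and which way it could err.

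**Inputs.** The documents give none of these; all values below are assumptions.
- p: share of high-risk subjects who self-identify from the instructions
- a: seeking rate among those who self-identify
- b: seeking rate among those who do not
- d: share of self-identified seekers who give no follow-up survey because they were dropped

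For simplicity, everyone who self-identifies is taken to be truly high-risk.

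**Target.** True rate among all high-risk subjects = p·a + (1 − p)·b. The survey never observes b, so this cannot be estimated without an assumption about b.

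**Step 1. Report the rate among those asked, with no seekers lost (d = 0).** The reported rate is a, and the error is a − [p·a + (1 − p)·b] = (1 − p)(a − b).

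With a = 20% and b = 0, the report says 20%. The true rate is:
- p = 0.9: 0.9 × 20% = 18%
- p = 0.7: 0.7 × 20% = 14%
- p = 0.5: 0.5 × 20% = 10%

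Setting b = 0 is the extreme case. With p = 0.7, a = 30% and b = 5%, the true rate is 0.7 × 30% + 0.3 × 5% = 22.5% and the error is 0.3 × 25 = +7.5 points. For p from 0.5 to 0.9, a from 10% to 50% and b from 0 to 10%, the error runs from 0 (a = b) to +25 points (p = 0.5, a = 50%, b = 0).

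**Step 2. Let dropped seekers go unsurveyed.** The reported rate becomes a(1 − d)/(1 − a·d). With p = 0.7, a = 30%, b = 5% (true rate 22.5%):

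| d | Reported rate | Error (points) |
|---|---|---|
| 0 | 30.0% | +7.5 |
| 0.3 | 0.21/0.91 = 23.1% | +0.6 |
| 0.5 | 0.15/0.85 = 17.6% | −4.9 |
| 0.8 | 0.06/0.76 = 7.9% | −14.6 |
| 1 | 0% | −22.5 |

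The sign changes where 0.30(1 − d) = 0.225(1 − 0.30d), that is d = 0.075/0.2325, about 0.32. Losing subjects who returned the device without seeking a study would remove non-seekers and push the rate back up; that is not modelled here.

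**Step 3. Use all STOP-BANG high-risk completers as denominator, counting the unasked as non-seekers (d = 0).** The reported rate is p·a = 0.7 × 30% = 21.0% against a true 22.5%, which is slightly low. If b = 0 it equals the true rate.

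**The case against.** The strongest reply is that the plan never says the rate will be computed among those asked. Data Collection says that STOP-BANG at follow-up is there to evaluate the response of high-risk subjects, so the natural denominator may be everyone who scores high. Those who missed their risk then stay in the denominator, and step 3 shows no overstatement. This stands against any claim that they drop out of the result. It does not supply their outcome: counting the unasked as non-seekers is an imputation that the plan does not state.

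Second, Methods and Procedures speaks of monitoring the subjects found high-risk by their own scoring. Response to the label is a coherent question for an over-the-counter simulation. But it is narrower than the objective in section II, and the two need to be reconciled.

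Third, the drop rule in the OSA section can reverse the bias, as step 2 shows. This also stands. It makes the rate harder to interpret; it does not repair the filter.

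A reader might also infer that the filter biases the result in the sponsor's favour. The documents do not support that. The theory in the Background section is that most patients are not making sleep-study appointments, and a low seeking rate would fit it.

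Finally, the attachments are not in the text reviewed, so the final survey wording could not be checked.

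**Conclusion.** The point holds as a gap in data collection. As described under Study Design, the survey does not collect the secondary outcome from high-risk completers who do not report self-identifying, although the objective covers them and STOP-BANG identifies them. The seeking rate among all high-risk subjects cannot be estimated from it.

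A reader might go further and say that the reported rate is overstated. That needs three things: a denominator of those asked, less seeking among non-identifiers, and no offsetting loss of seekers. The second is plausible, because people unaware of a risk have less reason to be tested. The first is not stated in the plan, and the drop rule puts the third in doubt. Where all three hold, the overstatement is (1 − p)(a − b): 2, 6 or 10 points in the 20% versus 0% illustration. The net direction is not determined by the documents.

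Confidence is medium. The point affects the secondary objective and leaves the primary analysis untouched. It should be fixed before the survey is fielded.

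**What to change.** 1. Remove the skip. Ask every follow-up respondent whether they sought medical care, enrolled in or completed a sleep study, returned the device, or continued to use it.
2. Send the same items to subjects dropped under the OSA section for seeking a study or returning the device, and count their answers. Removing the skip alone would not reach them if they receive no follow-up survey, and those who sought a study belong in the numerator.
3. Define the secondary denominator as all subjects scoring high-risk on Attachment D, including those dropped as high-risk under the OSA section.
4. Report separately the share of these who self-identified from the instructions. This keeps the label-response question as a result in its own right.
5. Reconcile the OSA section, Study Design, Methods and Procedures, and Data Collection on who is followed and how. In particular, the OSA section counts using the device among the outcomes, while the options in Methods and Procedures do not list it. Study Design also surveys subjects about sleep-study enrolment and discontinuation, while the OSA section drops those who seek a study or return the device.

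The cost is a change to the online survey logic, a short form for dropped subjects, and one sentence defining the denominator.

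### Sleep-study seeking is read once, in a survey emailed ten days after receipt, so high-risk users who act later cannot be told apart from those who never act.

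*Combined protocol and SAP*

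**What the plan says.** Section II (Purpose and Background) gives the secondary objective for patients at high risk of sleep apnea: "to determine whether they will seek a conclusive diagnosis with a sleep study". It sets no time horizon.

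The measurement is described in Study Design. On timing: "An email prompting them to complete a follow-up questionnaire will be sent ten days after the device has been received". On who is asked: "users will be asked if they self-identified (on the basis of the product instructions) as being at risk for OSA". On what is asked of those who say yes: "they will be asked about their response, including whether they sought medical care, enrolled in a sleep study, or discontinued use of the device". Methods and Procedures also places the survey email after ten days of use.

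Subjects can learn of their risk at two points. Methods and Procedures says: "The product instructions will contain a brief questionnaire (Attachment D, STOP-BANG Survey) assessing the subject's risk for OSA". Data Collection gives the same instrument again at follow-up: "The postquestionnaire will consist of Attachments B, C, and D, also allowing the study to evaluate the response of subjects at high risk of OSA".

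Methods and Procedures promises more generally: "The response of these subjects will be monitored to see how they respond and whether they continue to use the device or seek medical attention". It names no source or date other than the survey. Transition from Research Participation lets subjects go on using the device after the survey and describes no further contact. The Obstructive Sleep Apnea (OSA) section says that subjects who seek a sleep study or return the device are dropped. No section says whether they still receive the survey. No denominator, analysis or missing-data rule is given for this objective.

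**The concern.** The question has no time limit, but the answer is taken at one early point. A subject who tries the device for the ten requested nights, completes the survey and then books a study gives the same answers as a subject who will never book one. A subject whose risk first becomes apparent in the follow-up questionnaire has had no time to act on it.

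The Background section puts forward the sponsor's theory that most patients are not arranging sleep studies. A low figure at day 10 would seem to support that theory even if it came only from the short window. The objective is about what users will do, and a single reading at day 10 shows only what they have done so far.

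**Working it through.** **The plan's own figures.** None is stated for this objective. The sample size in Data Analysis and Monitoring (about 350 completers, 350 / 0.70 = 500 enrolled) concerns the VAS and does not bear on this point.

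**Inputs from the documents.** Survey email at day 10 after receipt; risk questionnaire in the product instructions, so at most about ten days of opportunity before that email; no later contact.

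**Inputs that must be assumed.** The documents give no seeking rate, no time to seeking and no number of high-risk subjects. Let p be the share who eventually seek, and let time to seeking among them be exponential with median m days, counted from receipt. The share of eventual seekers who have acted by day t is

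F(t) = 1 − 0.5^(t/m),

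and the proportion observed at day t is p × F(t). The last column takes p = 40% for illustration.

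| Assumed median m (days) | F(10) | F(90) | Day-10 reading if p = 40% |
|---|---|---|---|
| 5 | 0.750 | 1.000 | 30.0% |
| 10 | 0.500 | 0.998 | 20.0% |
| 21 | 0.281 | 0.949 | 11.2% |
| 30 | 0.206 | 0.875 | 8.3% |
| 45 | 0.143 | 0.750 | 5.7% |

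For example, with m = 21, F(10) = 1 − 0.5^(10/21) = 0.281 and 0.40 × 0.281 = 11.2%.

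**Direction.** F(10) cannot exceed 1 or F(t) for any later t. Truncation alone therefore lowers the figure, or at best leaves it unchanged, against any horizon beyond the survey. This does not depend on the exponential form; the sizes do.

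**Other influences.** If seekers are dropped and not surveyed, the figure falls further. With a true day-10 proportion of 20% and an assumed 25% of seekers missing, it reads 0.20 × 0.75 / (1 − 0.20 × 0.25) = 15.8%. With 50% missing it reads 0.10 / 0.90 = 11.1%. In the other direction, self-report, and asking only those who identified themselves as at risk, could raise it. The documents allow none of these to be sized.

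**Check on the remedy.** Take m = 10 and assume that half of subjects answer a day-90 email, independently of seeking. If every non-responder is counted as not seeking and earlier answers are ignored, day 90 recovers 0.5 × 0.998 = 0.499 of eventual seekers, no better than day 10. If an earlier yes is carried forward, it recovers 0.500 + 0.5 × (0.998 − 0.500) = 0.749. The responders-only figure corresponds to 0.998. A later email therefore helps only if earlier answers are kept and both figures are shown.

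**The case against.** The strongest reply is that the plan studies the immediate response to the instructions in a simulated over-the-counter purchase. The OSA section lists three behaviours: seek a study, return the device, or use it. A subject who uses it for ten days is correctly placed in the third. No rule in the documents labels that subject as someone who will never seek a study. If only ten-day behaviour is meant, there is no truncation bias. That is right, but Section II does not limit the objective in this way, so at a minimum the limit has to be written down.

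The measure is also broader than a completed test. Methods and Procedures words one option as "complete a full, overnight in-office sleep study", but the survey also counts having sought medical care or enrolled. Subjects waiting for an appointment are therefore not lost; only those who have not yet acted are. Day 10 is when the email goes out. No completion window is stated, so some answers will come later. Both points stand and reduce the loss.

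A reader might infer that the reading is taken while subjects are still asked to wear the device. Methods and Procedures places it after the ten days of use.

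It can also be said that a high-risk subject who carries on for ten nights is outside the options in Methods and Procedures, which do not list continued use. Yet the end of the same paragraph, and the OSA section, expect that some will continue. Those passages should be reconciled. Meanwhile, continued use is a behaviour that the plan itself sets out to observe.

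Finally, the medians are assumed, and a discounted home study offered in the instructions could make action quick. That is why the table starts at 5 days, where three quarters of eventual seekers are captured.

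**Conclusion.** The point holds as a limitation of the secondary objective. The described data cannot separate users who have not yet sought a sleep study from those who will not. Against a longer horizon, truncation can only lower the proportion. Under assumed exponential times with medians from 5 to 45 days, the day-10 survey captures from about 75% down to 14% of eventual seekers. The range rests wholly on those assumptions.

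Two stronger readings are tempting. One is that the secondary result is biased low overall. The documents do not support this: only truncation has a fixed direction, and self-report and the restriction to self-identified subjects may work the other way. The other is that later follow-up would show whether an over-the-counter device keeps people from a sleep study, a concern raised in Background. It would not, because a single-arm proportion has no comparator at any time point.

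The primary endpoints and sample size are unaffected. This is an inexpensive improvement, not a defect in the main analysis.

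**What to change.** State the time horizon and denominator for the secondary objective. Then send one automated email at a pre-specified later date, for example about 90 days after receipt, to all subjects who screened high risk. This means those who identified themselves from the instructions, those who score high risk in the follow-up questionnaire, and those dropped under the OSA section. Ask whether, and on what date, they sought care, enrolled in a sleep study or completed one.

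Report the cumulative proportion with a 95% confidence interval at day 10 and at the later date. Carry forward any earlier yes. At the later date show two figures side by side: one among those who answered the later email (numerator and denominator both restricted to them), and a bound that counts non-responders without an earlier yes as not seeking. The bound should not stand alone as the main figure.

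The cost is one email to a subset whose contact details Attachment A already collects, a change to the consent wording, and a later secondary result. Response will probably be lower once the refund has been paid. The primary timeline does not change.

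If the email is not added, limit the conclusion to seeking by the day-10 survey, and do not present it as evidence that users will not seek a sleep study. In either case, say that the proportion does not show whether the device causes people not to seek one.

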# Data Analysis and Monitoring

The primary endpoints, a VAS assessment of snoring and the Snoring Severity Scale will be analyzed using a two-sample *t*-test comparing the pre-study and post-study questionnaire results. The ANCOVA method may also be used to evaluate the impact of different variables, like age, weight, gender, or others, on the study results. There are no potential serious risks to patients, and no stopping criteria that need to be analyzed during the study.

In determining sample size, it was estimated that the device would produce a 15% improvement in snoring, as measured on the VAS. With a level of significance of p < 0.05 and a power of 80%, approximately 350 subjects will need to complete the study to generate statistically significant data. Assuming a 30% dropout rate for non-compliance with the study or the discovery of moderate to severe sleep apnea, 500 subjects will be enrolled in the study to ensure the study is adequately powered.

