## Data Storage and Confidentiality

Data will be collected via a password-protected website and confidential email forms. The results will be securely stored in password-protected cloud storage and then downloaded onto a personal computer to be compiled in Excel. Once transferred to Excel, the data will also be placed into a password-protected file. This data will be available to the study coordinator alone, as the principal investigator is blinded (a precaution since he has a financial interest in the device). Subject identifiers will be necessary, but only the study coordinator will have access to the data with subject identifiers. These identifiers will be removed before any data or statistical analysis is conducted. The principal investigator will be provided the subject identifier and data for any patient that has an unexpected serious reaction to use of the device for analysis and response as well as notification of regulatory bodies and the investigational review board.

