## Statistical Analysis

A two-sample *t*-test will be used to compare the results from the pre-trial and post-trial questionnaires. Statistical significant will be set at a 95% confidence level (p < 0.05).

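### The primary test is named as a two-sample t-test, but one group is measured twice; a paired t-test on each subject's change should be named

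*Combined protocol and SAP*

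**What the plan says.** The trial has one group and no control arm. Under Data Collection, "The pre-questionnaire will consist of Attachments A, B, and C to establish a baseline"; the post-questionnaire contains Attachments B (VAS) and C (Snoring Severity Scale) again, together with D. Each completer therefore gives two values on each primary endpoint.

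The analysis is named in three places:

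- Study Design: "A two-sample t-test will be used to analyze the change from the initial survey to the follow-up survey", followed by "with patients serving as their own controls".
- Data Analysis and Monitoring: a two-sample t-test for both primary endpoints, "comparing the pre-study and post-study questionnaire results". ANCOVA is optional there, to look at the influence of variables such as age, weight and gender. It does not replace the primary test.
- Statistical Analysis: a two-sample t-test that "will be used to compare the results from the pre-trial and post-trial questionnaires", at p < 0.05. The own-controls wording is not repeated here.

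The word paired does not appear. On sample size, Data Analysis and Monitoring says "it was estimated that the device would produce a 15% improvement in snoring, as measured on the VAS" and, with 80% power, "approximately 350 subjects will need to complete the study to generate statistically significant data". With 30% dropout this becomes 500 enrolled. No SD, SD of change, pre/post correlation, sidedness or formula is given, and it is not stated whether the 15% is relative or in scale points.

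**The concern.** A two-sample t-test treats its two sets of values as coming from different people. Here they come from the same people, and scores from one person on one scale are usually positively correlated. The literal test then uses a standard error without the covariance term. Its p-values and confidence intervals do not describe the change that was measured.

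With positive correlation, and the same subjects on both sides, the error makes the test conservative. It does not create false positives, but it can miss a real reduction in snoring. Whether the planned 80% power survives depends on which formula produced 350.

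An unpaired test also does not require matched records. Nothing in its name stops an analyst from comparing all 500 baselines with about 350 follow-ups, and then the two means describe different sets of people.

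**Working it through.** **The plan's own figures.** Enrolment reproduces: 350 / (1 − 0.30) = 500. The 350 cannot be derived, because no SD is given. If the effect is read in SD units (an assumption), with two-sided alpha 0.05 and 80% power (1.96 + 0.84 = 2.80), two calculations match it:

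- Paired test, 0.15 SD of change: (2.80/0.15)² gives 349 pairs.
- Two independent groups, 0.30 SD: 2 × (2.80/0.30)² gives 175 per group, 350 in total.

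A two-sample test at 0.15 SD would need 698 per group. The match therefore does not settle which test was intended.

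**Standard error and type I error.** Take n pairs, equal SD σ and correlation ρ. The true variance of the mean change is 2σ²(1 − ρ)/n; the two-sample formula uses 2σ²/n. Hence:

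- standard error inflation = 1/√(1 − ρ)
- true type I error = 2 × [1 − Φ(1.96/√(1 − ρ))]

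**Power at 350 completers under two sizing assumptions.**

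*Sized as paired:* the effect is 2.80/√350 = 0.150 SD of change.

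- Literal two-sample power = 1 − Φ(1.96/√(1 − ρ) − 2.80)
- Completers the literal test needs for 80% = [(1.96/√(1 − ρ) + 0.84)/0.150]²
- The paired test has 80% by construction

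*Sized as two-sample, 350 values per time point:* the effect is 2.80 × √(2/350) = 0.212 SD of score.

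- Literal power = Φ(0.84/√(1 − ρ))
- Paired power = Φ(2.80/√(1 − ρ) − 1.96)
- Pairs needed for 80% = 350 × (1 − ρ)

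| Assumed ρ | 0.3 | 0.5 | 0.7 |
|---|---|---|---|
| Standard error inflation | 1.20 | 1.41 | 1.83 |
| True type I error, literal test | 1.9% | 0.56% | 0.03% |
| Sized as paired: literal power | 68% | 51% | 22% |
| Sized as paired: completers for 80%, literal test | 453 | 583 | 872 |
| Sized as two-sample: literal power | 84% | 88% | 94% |
| Sized as two-sample: paired power | 92% | 98% | 99.9% |
| Sized as two-sample: pairs for 80%, paired test | 245 | 175 | 105 |

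Simulation with 20,000 trials per setting agrees: two-sample type I error was 1.8%, 0.58% and 0.04%, and the paired test stayed at 4.7–5.0%. Simulated powers were within about one percentage point of the table.

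**Unmatched records, an illustration.** If the 30% who do not complete had baseline scores 0.3 SD worse (assumed), using all baselines would shift the pre mean by 0.30 × 0.3 = 0.09 SD with no individual changing. Limiting the test to each completer's own change removes that mismatch.

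**The case against.** The strongest reply is that this is only a loose label. Study Design speaks of change and of own controls, which describes a paired analysis, and 349 pairs at 0.15 SD lies close to 350. That may well be what was meant. But Statistical Analysis, where an analyst would look, has only the two-sample label, and the 175-per-group match leaves the intention open.

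The size of the harm can also be challenged, and much of this stands:

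- The fall to 68%, 51% and 22% needs sizing and analysis to disagree: sized as paired, run as two-sample. If both are paired, power is 80%; if both are two-sample with 350 per time point, it is 84–94%.
- If 350 meant 175 per group at 0.30 SD, 350 values at each time point would give the literal test over 99% power at these correlations.
- The steep fall with ρ comes from holding the SD of change fixed, so the effect in score SDs shrinks from 0.177 to 0.116. With the effect fixed at 0.15 score SD, literal power is about 51–52% at each ρ, against 66%, 80% and 95% for the paired test.
- With 500 baselines and 350 follow-ups, random dropout and equal SDs, the inflation is 1.15, 1.30 and 1.54; type I error about 2.4%, 1.1% and 0.26%; and sized-as-paired power about 75%, 60% and 32%.

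These points change the size of the loss, not its direction. At zero correlation the two tests are equivalent and nothing is lost.

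**Conclusion.** The concern holds and should be fixed. The named test contradicts the design in all three places where it appears, and that conclusion needs no outside figure.

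The cost depends on a positive pre/post correlation, which the documents do not give. For 0.3 to 0.7, with equal SDs and 350 completers on both sides, the standard error is 1.20 to 1.83 times too large and the test runs well below its 5% level. Whether 80% power is lost cannot be decided from the documents. A paired test holds the 5% level and has at least 80% power under either sizing assumption in the table when the correlation is zero or positive.

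This does not show that 350 or 500 is too small; that needs an SD of change. Nor does a paired test supply a concurrent control or remove selection in who completes.

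**What to change.** 1. In Study Design, Data Analysis and Monitoring, and Statistical Analysis, replace the two-sample t-test with a paired t-test: a one-sample t-test on each completer's post-minus-pre change, limited to subjects with both questionnaires and reported with its 95% confidence interval.
2. In Data Analysis and Monitoring, state that 350 is a number of pairs. Give the SD of change, the sidedness, and the unit behind the 15%.
3. Data Storage and Confidentiality says "These identifiers will be removed before any data or statistical analysis is conducted". Add one sentence saying that a non-identifying study code links each subject's two records afterwards. The present text does not show that the link is broken; it only leaves it unstated.

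Item 1 is the essential change; items 2 and 3 fill in detail. The cost is wording in four sections and one study-code column in the analysis file. Data collection does not change. The wording should be settled before results are seen, because the two tests can give different answers on the same data.
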